1 PROTOCOL SYNOPSIS

Title	Partial Responders to PPI treatment: the Cost to Society and the Burden to the Patient – a study in France (REMAIN Study –French Arm)
Protocol Number	Study code D9120N00013
Study design	French arm of a multi-center, prospective, observational, non interventional study
Patients	Patients with Gastroesophageal Reflux Disease (GERD) newly classified as partial-responders to proton pump inhibitors (PPIs)
Period for Patient Participation	
Primary objectives	
– To describe common treatment pathways, including extent of and time to referral to specialists;– To collect resource utilization data;– To collect relevant cost estimates and calculate cost per patient;– To assess the symptom load, impact of symptoms on daily life and effect on work productivity.
Secondary objectives	
– To estimate the proportion of new partial-responders to all new patients with GERD
Inclusion criteria	
1. Provision of signed informed consent.2. Able to read and write in French and able to comply with study requirements.3. Female or male, aged 18 years or above.4. The patient must at the enrolment visit be identified for the first time as partial responder to PPI treatment as defined by the following criteria:
a) At least 6 month history of GERD symptoms (need not be consecutive)b) Continuously treated with unchanged optimized PPI treatment for any GERD indication during the last 4 weeks (an optimized PPI treatment is a treatment, which according to the investigators judgment cannot be further improved by changing brand or dosing of the PPI) .c) Patients with a history of reflux (erosive) esophagitis Los Angeles grade A-D must have been continuously treated with a PPI during the last 8 weeks before enrolment (optimized PPI treatment during the last 4 weeks before enrolment).

	
5. To be eligible for enrolment, the patients must have reported, in the RDQ-RI screening instrument using 7 days recall, a minimum of three days with at least one of the two following symptoms with at least moderate severity:
 
 • a burning feeling behind the breastbone • an unpleasant movement of material upwards from the stomach.
Exclusion criteria	
 1. Patients that have not experienced any GERD symptoms improvement at all during PPI treatment. 2. Prior surgery of the upper GI tract (open, endoscopic and laparoscopic surgery on the esophagus, the stomach and the duodenum with the exception of over sewing or endoscopic treatment of an bleeding ulcer) 3. Any other condition which in the opinion of the investigator would render the patient unsuitable for inclusion in the study. 4. Involvement in the planning or conduct of the study. 5. Previous enrolment in the present study. 6. Involvement in any other observational study or in any clinical study at the time of this study or during the last 6 months.
Primary and secondary endpoints	
Frequency and severity of GERD symptoms
 
Quality of Life
 
Productivity loss
 
Healthcare resource use (primary care visits, secondary care visits, medications, diagnostic tests, surgeries, etc.)
 
Utility values

Patient-reported Outcome Instruments	
Reflux Disease Questionnaire – Reflux Inhibition (RDQ-RI)
 
GERDQ
 
Quality of Life in Reflux and Dyspepsia – Reflux Inhibition (QOLRAD-RI)
 
EQ-5D
 
Short Form 36 (v2)
 
HADS
 
Work Productivity and Activity Impairment for Patients with Gastroesophageal Reflux Disease (WPAI-GERD)
 
Resource Utilization Questionnaire

Sample size	275 enrolled partial-responders to PPI for the treatment of GERD (200 completed subjects)
Procedures	Patients will be recruited by their physicians during a regularly scheduled office visit. The physician will recruit patients into the study who are

	
identified for the first time as partial responders to PPI treatment. Patients will be asked to complete a self-administered questionnaire at the recruitment visit and every 3 months for a total period of 12 months thereafter. Follow-up questionnaires will be sent to the patient's place of residence. Physicians will collect the patient's medical history, demographics and co morbidities in a paper CRF at the recruitment visit and will collect information from medical records on health resource use every 6 months for a total of 12 months per patient. In addition, the physician will keep a log of all new patients with GERD seen at their office during the enrollment period in order to allow for an estimate of the ratio of partial responders to all new patients with GERD.

Statistical considerations	
Due to the descriptive objectives of the study, there are no hypotheses to test with statistical methods to predetermine a required sample size. The choice of target sample is therefore pragmatic guided mainly by sample sizes in previous similar studies

Study glossary

AZ	AstraZeneca R&D, Mölndal, Sweden
CRF	Case Report Form
CNIL	Commission Nationale Informatique et Liberté
CNOM	Conseil National de l'Ordre des Médecins
CCTIRS	Comité Consultatif sur le Traitement de l'Information en matière de Recherche dans le domaine de la Santé
GCP	Good Clinical Practice
GEP	Good Epidemiological Practice
GERD	Gastro Esophageal Reflux Disease
GERDQ	Questionnaire for patients with symptoms in the upper gastrointestinal tract
GP	General Practitioner
HADS	Hospital Anxiety and Depression Scale
ICF	Informed Consent Form
ICH	International Code of Harmonization
ISF	Investigator Study File
PCP	Primary Care Physician
PPIs	Proton Pump Inhibitors
PRO	Patient Reported Outcomes
QOLRAD-RI	Quality of Life in Reflux and Dyspepsia – Reflux Inhibition
RDQ-RI	Reflux Disease Questionnaire – Reflux Inhibition
SAE	Serious Adverse Event
SF-36	Short Form 36
SOP	Standard Operating Procedures
TLESR	Transient Lower Esophageal Sphincter Relaxation
WPAI-GERD	Work Productivity and Activity Impairment – Gastro-Esophageal Reflux Disease

2 BACKGROUND AND RATIONALE

Gastroesophageal reflux disease (GERD) is one of the most common gastrointestinal disorders worldwide. It is estimated that approximately 20% of the Western population suffers from GERD symptoms at least weekly¹, but this figure may underestimate the true prevalence, since many patients self-medicate and do not seek medical attention.² Others are not aware that they have GERD.³ According to Bardhan *et al*⁴ the mean age of patients at presentation with GERD is 53.5, with a slight preponderance among males (55% vs. 45%).

GERD is characterized by reflux of the stomach contents into the esophagus, oropharynx, larynx, or airway. The primary etiology is transient lower esophageal sphincter relaxation (TLESR), however, other mechanisms may include decreased LES resting pressure, impaired esophageal clearance, delayed gastric emptying, decreased salivation, or impaired tissue resistance⁵.

Symptoms of GERD include heartburn, regurgitation, and dysphagia, as well as extra-esophageal or atypical manifestations such as cough, asthma, laryngitis, or non-cardiac chest pain⁶. Potentially serious esophageal complications can include esophagitis, esophageal ulcers, esophageal stricture or obstruction, Barrett's esophagus or esophageal cancer, as well as extra-esophageal diseases such as respiratory problems, chest pain, angina, and increased mortality in the year after diagnosis.⁷ In addition to the physical ramifications of the disease, GERD sufferers report significant treatment burden and negative impact of the disease on quality of life.⁸

The diagnosis of GERD is often made subjectively when symptoms respond to acid suppressive therapy⁹ with H-2 receptor antagonists, or proton pump inhibitors (PPIs), though additional confirmatory diagnostic tests include 24-hour pH monitoring, endoscopy, biopsy, barium swallow, laryngoscopy, and esophageal motility testing. Endoscopy is the gold standard to definitively diagnose erosive esophagitis.

PPIs and Partial Response

Therapy with a PPI is currently considered the most effective way to relieve symptoms and to help promote esophageal healing in GERD. Since GERD is a chronic disease that often relapses, long-term maintenance therapy with a PPI is usually necessary¹⁰; however, some patients continue to experience symptoms despite PPI therapy.¹¹

Non-acid reflux has been identified as one of the causes of persistent symptoms despite PPI therapy and it is estimated that weakly or non-acidic reflux episodes play a major role in eliciting symptoms in 30-40% of patients on PPI therapy. It is for this reason medications that inhibit TLESR (e.g., baclofen) can be used as a therapeutic option; however, its use is limited due to side effects¹². There are also anti-reflux surgical procedures that tighten the lower esophageal

sphincter and inhibit TLESR (e.g., fundoplication, endoscopic Stretta procedure), but the benefits are limited by the costs,¹⁴ surgical risks,¹⁵ and, at times, long term efficacy¹⁶.

Health-related quality of life on medication remains significantly impaired in partial-responders compared to good responders, as measured with both generic and health-specific questionnaires.¹⁷ In addition, information concerning the frequency and severity of symptoms in this group of patients is limited, and there are currently no guidelines available for treatment.

Because of this lack of research studies on the burden of illness to partial-responders, results from this observational cost and burden of illness study in PPI partial-responders is expected to provide important empirical data to support further knowledge about this patient population.

3 STUDY OBJECTIVES

3.1 Primary Objectives

The primary objectives of this observational, prospective study are

- to describe common treatment pathways, including extent of and time to referral to specialists
- to collect resource utilization data
- to collect relevant cost estimates and to calculate the cost per patient
- to assess the symptom load, impact of symptoms on daily life and effect on work productivity
- to assess the effect of partial response on HRQoL

in patients with GERD newly identified as partial responders to PPI treatment.

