5 SUBJECT POPULATION

The target population for this study is adults, aged 18 and older, who are suffering from GERD and are newly diagnosed as partial responder to optimized PPI treatment. Subjects must meet all of the following inclusion criteria to be eligible for enrollment into the study:

Inclusion Criteria:

1. Provision of signed informed consent.
2. Able to read and write in French and able to comply with study requirement.
3. Female or male, aged 18 years or above.
4. The patient must at the enrolment visit be identified for the first time as partial responder to PPI treatment as defined by the following criteria:
 - a) At least 6 month history of GERD symptoms (need not be consecutive)
 - b) Continuously treated with unchanged optimized PPI treatment for any GERD indication during the last 4 weeks (an optimized PPI treatment is a treatment, which according to the investigators judgment cannot be further improved by changing brand or dosing of the PPI) .
 - c) Patients with a history of reflux (erosive) esophagitis Los Angeles grade A-D must have been continuously treated with a PPI during the last 8 weeks before enrolment (optimized PPI treatment during the last 4 weeks before enrolment).
5. To be eligible for enrolment, the patients must have reported, in the RDQ-RI screening instrument using 7 days recall, a minimum of three days with at least one of the two following symptoms with at least moderate severity:
 - a burning feeling behind the breastbone
 - an unpleasant movement of material upwards from the stomach.

Exclusion Criteria:

1. Patients that have not experienced any GERD symptoms improvement at all during PPI treatment.
2. Prior surgery of the upper GI tract (open, endoscopic and laparoscopic surgery on the esophagus, the stomach and the duodenum with the exception of over sewing or endoscopic treatment of an bleeding ulcer)

-
3. Any other condition which in the opinion of the investigator would render the patient unsuitable for inclusion in the study.
 4. Involvement in the planning or conduct of the study.
 5. Previous enrolment in the present study.
 6. Involvement in any other observational or clinical study at the time of this study.

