10.2 Study Population

Two study populations are considered: the “log population”, which consists of all GERD patients approached for this study and the “per protocol population”, which consists of all patients enrolled in the study, satisfying to inclusion and exclusion criteria specified in section 5.

The proportion of partial-responders to PPI and analysis of screening failure will be conducted over the log population and the analyses of symptoms, patients reported outcomes, healthcare

resource use, productivity loss and associated costs will be performed on the per protocol population.

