10.7 Cost of Illness Analysis

The first step of this analysis will consist of estimating the size of the target population. A literature review will be undertaken to obtain the incidence and prevalence of GERD in France and the proportion of patients treated in primary care and secondary care. The proportion of

patients with GERD with incomplete response to PPI will be calculated from the sites' log. The proportion of partial responders will be reported by site, physician type and overall, together with 95% confidence intervals. The size of the target population (partial responders to PPI) in France will then be derived.

Based on the information obtained from the cost of healthcare resources collected alongside this study, we will be able to estimate the cost of partial response to PPI within the year of partial response diagnosis. Some assumptions will be made on the basis of the literature and clinical experts' opinion to estimate the mean cost of treatment over subsequent years. The cost of partial response to PPI will be reported overall and by type of resource (GP visits, specialist visits, diagnostic tests, hospitalization, prescribed medications and OTC medications) for France.

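### HRQoL and cost are measured only in partial responders, so the plan can describe them but cannot estimate an effect of partial response on HRQoL (3.1) or a cost attributable to it (10.7)

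*Protocol*

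**What the plan says.** Protocol section 3.1 lists five primary objectives. The last is "to assess the effect of partial response on HRQoL". The list closes by placing all five "in patients with GERD newly identified as partial responders to PPI treatment". The synopsis gives only the first four; quality of life appears there as an endpoint but not as an objective.

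Partial-responder status is an entry condition (section 5): "The patient must at the enrolment visit be identified for the first time as partial responder to PPI treatment". Section 10.2 assigns the patient-reported outcomes and costs to one group: "resource use, productivity loss and associated costs will be performed on the per protocol population", a population that "consists of all patients enrolled in the study, satisfying to inclusion and exclusion criteria specified in section 5".

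Section 10.7 says that "we will be able to estimate the cost of partial response to PPI within the year of partial response diagnosis". It then reports that cost for France, overall and by type of resource, and extends it to later years by assumption.

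**The concern.** An effect of partial response, or a cost caused by it, is a difference between partial responders and comparable GERD patients who respond to a PPI. In this design, partial response is both the exposure named in the objective and the condition for entering the study, so it does not vary among the patients who supply HRQoL or cost data.

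What is at stake is the conclusion. A report that follows section 3.1 literally would present an HRQoL level as an effect. One that follows section 10.7 would present the whole GERD-related cost of these patients as the cost of their partial response, for France as well as per patient.

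**Working it through.** The protocol gives no HRQoL or cost figure to reproduce, so the check is which group carries which data.

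**1. Who could supply a comparison**

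- *Enrolled patients (sections 5, 10.2).* HRQoL, productivity, resource use and cost are all available. Every patient is a partial responder.
- *Log of newly diagnosed GERD patients (section 7.7).* The fields are year of birth, gender and dates. There is no HRQoL, resource use or cost.
- *Screening failures (section 7.4).* Baseline CRF pages are kept, and the RDQ-RI where all other entry criteria are met. No HRQoL instrument or follow-up is stated for them.
- *External reference.* No responder cohort or population norm is named for HRQoL or cost. The literature review in section 10.7 covers incidence, prevalence and care setting; literature and expert opinion are used for costs in later years.
- *The same patients earlier.* HRQoL is first measured at visit 1 (section 7.9), when partial response is already established. Some treatment history is collected retrospectively (section 10.3), but with no stated look-back window and no planned before/after contrast.

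**2. HRQoL**

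Effect = mean in partial responders − mean in responders.

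- First term: about 200 completers (section 6) give a 95% half-width of 1.96 × SD/√200 = 0.139 SD, ignoring clustering by site.
- Second term: n = 0. The difference has no estimator, and enrolling more partial responders would not supply one.

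**3. Do the models in section 10.6 fill the gap?**

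They relate symptom frequency and severity, and change in them, to HRQoL and cost within the cohort. That is an association with symptoms among partial responders. Entry requires at least moderate symptoms on three or more of the last seven days, so later improvement may partly be regression to the mean.

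**4. Cost**

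Sections 7.6 and 7.9.1 have the physician record resource use related to GERD, including all GERD prescriptions. Criterion 4b puts every patient on continuous PPI at entry, and section 2 says that long-term PPI maintenance is usually needed in GERD generally. Part of the recorded cost would therefore be expected with a full response too.

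Let C be the gross cost per patient and f the share of C that a responder would incur (unknown, taken between 0 and 1):

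Attributable cost = C × (1 − f)

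- f = 0: 100% of C
- f = 0.25: 75%
- f = 0.5: 50%
- f = 0.75: 25%
- f = 1: 0%

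Nothing the study collects informs f. If the national figure is C times the number of partial responders, as section 10.7 implies, the same factor (1 − f) carries through to it.

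**The case against.** The best defence is context. The closing phrase of 3.1 confines every objective to this cohort. Section 6 calls the objectives descriptive, with no hypotheses, and no section promises a contrast with responders. Section 2 reports that "Health-related quality of life on medication remains significantly impaired in partial-responders compared to good responders", but cites this as an existing finding; the gap it names is the burden on partial responders, which one cohort can address. On this reading, the word effect is only loose. That is probably the intended meaning, and it supports rewording the objective. As written, though, a primary objective still claims an effect.

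Several narrower points stand:

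- Gross GERD-related cost in the affected patients is a proper cost-of-illness result and meets the cost-per-patient objective. Section 10.7 already splits it by resource type, with prescribed medications as a separate line.
- QOLRAD-RI asks about upper gastrointestinal symptoms and WPAI-GERD about impairment due to GERD, so contamination by comorbidity is mainly an issue for SF-36 and EQ-5D. Even so, the disease-specific scores do not show what responders would score.
- An analysis plan could name an external reference. It could not create a responder group inside the study.

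A reader might go further and infer that the national cost is overstated by some stated multiple. For example, an assumed background share of 30% to 60% gives 1/0.7 = 1.4 to 1/0.4 = 2.5. The protocol contains no cost figure and no basis for that share, so the multiple carries no weight. A reader might also infer that subtracting the entry PPI leaves the attributable cost. It does not: the PPI cost of a full responder is unknown, and the entry regimen is an optimized one that a responder need not share.

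**Conclusion.** The point holds as a mismatch between what sections 3.1 and 10.7 claim and what the design can estimate. For HRQoL, the contrast is not estimable from study data at all. For cost, the obtainable figure is sound, but its label invites an attribution that it cannot support. The gap between gross and attributable cost cannot be sized from the protocol; its direction rests only on responders incurring some GERD cost, which section 2 makes plausible.

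It does not follow that the cost analysis is invalid, or that any planned table, data item or sample size is wrong. The within-cohort results remain useful under an accurate description.

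**What to change.** - **Section 3.1:** reword the last objective to *describe HRQoL over 12 months in partial responders*, and reconcile the synopsis, which omits it.
- **Section 10.7:** label the per-patient and national figures *GERD-related cost of patients with partial response*, and state that they are not incremental versus PPI responders. Section 7.9.2 does not restrict the patient-reported over-the-counter item to GERD remedies, so say beside the label which of these products are counted.
- **Optional:** show PPI cost as its own line within prescribed medications. PPI type, dosage and prescriptions are already on the CRF. Do not present the remainder as the attributable cost.

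The cost is a few lines of wording and, if wanted, one extra table line from data already collected. The downside is a narrower claim. Keeping the present wording would require a named responder group or external reference with HRQoL and cost data, which is a larger change.

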3.2 Secondary Objective

The secondary objective of this study is to estimate the proportion of patients with GERD being identified for the first time as partial responders to optimized PPI treatment, to all patients newly diagnosed with GERD.

4 STUDY DESIGN OVERVIEW

This is a multi-center, 12 months prospective study in France. Approximately 275 adult (18 years or older) patients with GERD who have been identified for the first time as partial responders to optimized PPI treatment will be enrolled at approximately 30 sites in France to obtain an evaluable target sample size of 200 patients, assuming an estimated 30% attrition rate over the course of the study.

Patients will be enrolled at a regularly scheduled office visit. At this regularly scheduled office visit, the study physician or designated staff will invite potentially eligible patients to participate in the study. Patients will be provided with a written study description and copy of the informed consent form to review. Eligible patients who express an interest in participating will be officially enrolled in the study on the day of the office visit.

Enrolled patients will fill out a self-administered paper patient survey during this visit including questions for their quality of life and symptoms severity.

Physicians will complete the enrollment part of the CRF including patient demographics and confirmation of patient's eligibility. They will also keep a log of all newly diagnosed patients with

GERD seen during the enrollment period in order to provide estimates of the ratio of patients with GERD identified for the first time as partial responders to optimized PPI treatment to all newly diagnosed patients with GERD. The physician will follow the patients through a period of 12 months after enrollment collecting data from the patient medical records at baseline, month 6 and month 12.

The patient will receive a set of questionnaires every 3 months during the same 12 month period after the first visit. This survey will include questions relating to resource utilization (over the counter medication and visits to other physicians), as well as questionnaires relating to the patient's quality of life and symptom frequency and severity.

